### 8.2 General Considerations

- a. Missed doses are to be omitted rather than made up.
- b. If multiple toxicities are seen for any given single agent, administer dose based on greatest reduction required for any single toxicity observed.

- c. Reductions apply to the treatment given in the preceding cycle and are based on toxicities observed since the prior dose.
- d. Once dose is reduced, patients will continue at new dose. No dose re-escalations are allowed.
- e. If the patient vomits after taking the tablets, the dose is replaced only if the tablets can actually be seen and counted.
- f. Use of G-CSF and erythropoietin for patients being treated on this study is at the discretion of the treating physician. If used, it must be documented in the "Notes" section of the **S1107** Treatment Form.

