### 8.5 ARQ 197 Dose Modification

If ARQ 197 is held, erlotinib will also be held for patients on Arm 2 and resumed at the same time treatment with ARQ 197 is resumed. There will be no dose reduction of erlotinib if the toxicity was thought to be related to ARQ 197.

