#### a. Hematologic toxicities:

Absolute neutrophil count (ANC) ( $\times 10^6/L$ )	Platelets ( $\times 10^6/L$ )	ARQ 197
$\geq 1,000$ and	$\geq 75,000$	100% dose
$< 1,000$ or	$< 75,000$	*Hold until ANC $\geq 1,000$ and platelets $\geq 75,000$ and reduce to the next lower dose level

\* Treatment may be held up to 21 days and can be resumed at the next lower dose level once ANC is  $\geq 1000 \times 10^6/L$  and platelet count is  $\geq 75,000 \times 10^6/L$ . Patients who cannot tolerate ARQ 197 at 120 mg BID will be removed from the protocol. No dose re-escalation is allowed.

CLOSED TO PUBLIC 05/29/2014

b. Non-hematologic toxicities:

The following modifications should be followed in the event of ARQ 197 related-non-hematologic toxicity.

Toxicity Grade(NCI CTCAE v4.0)	Percent of full dose of ARQ 197I
0-2	100%
3	Hold*
4	Hold*

\* Treatment may be held up to 21 days Any patient who experiences Grade 3 or greater non-hematologic toxicity which resolves to Grade 0 or 1 may be treated at a next lower dose level of ARQ 197 for subsequent doses. Patients who cannot tolerate ARQ 197 at 120 mg BID will be removed from the protocol. No dose re-escalation is allowed.

c. ARQ 197 Dose Level Reductions

Starting Dose	First Reduction	Second Reduction
360 mg BID	240 mg BID	120 mg BID

NOTE: Any patient who fails to tolerate treatment of 120 mg BID will be withdrawn from protocol treatment. If a treatment is delayed more than 21 days for the resolution of ARQ 197-related toxicities to Grade 0 or 1 patient will be removed from the protocol.

CLOSED EFFECTIVE 05/29/2014

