8.6 Erlotinib Dose Modificationa

Toxicity (NCI CTCAE v4.0)	Dose Modification
Diarrhea	
Grade 1	None. Initiate therapy with loperamide.(8.7a)
Grade 2	Hold erlotinib. Initiate loperamide until resolution to Grade 0-1. Resume therapy at the same dose.
Grade 3 b or 4 b	Hold erlotinib. Initiate therapy with loperamide and appropriate supportive care until resolution to Grade 0 or 1 and then restart at 1 dose level lower
Rash	
Grade 1	None
Grade 2	None. Initiate treatment (8.7b) . If rash persists and is intolerable or worsens over 10 – 14 days, then reduce by 1 dose level.
Grade 3	Reduce by 1 dose level. If rash persists or worsens over 10 – 14 days, then interrupt erlotinib until resolution to Grade 0, 1 or 2 and then restart 1 dose level lower.
Grade 4	Permanently discontinue erlotinib.
Interstitial Lung Disease	
Any Grade	If ILD is suspected, erlotinib should be interrupted immediately pending diagnostic evaluation. If ILD is diagnosed, erlotinib should be discontinued permanently and appropriate treatment instituted as necessary.
Other Toxicities Attributable to Erlotinib	
Grade 1 or 2	None
Grade 3 or 4 b, c	Interrupt erlotinib until resolution to Grade 0 or 1 and then restart 1 dose level lower.
Other Toxicities (hematologic and non-hematologic) attributable to ARQ 197	
Grade 1 or 2	None
Grade 3 or 4	Hold erlotinib until ARQ 197 is resumed. If toxicity was deemed related to ARQ 197 no dose reduction of erlotinib is indicated

- (a) Doses that have been reduced should not be re-escalated. Any patient who fails to tolerate treatment at 50 mg/day will discontinue erlotinib and continue on single agent ARQ 197.
- (b) If the event does not resolve to Grade 0 or 1 within 21 days, erlotinib will be discontinued and patient will continue on a single agent ARQ 197
- (c) Only if  $\geq 2$  Grade level change from baseline

Erlotinib Dose Level Reductions

Starting Dose	First Reduction	Second Reduction
150 mg/day	100 mg/day	50 mg/day

NOTE: Any patient who fails to tolerate erlotinib at 50 mg/day will continue on single agent ARQ 197. If a treatment is delayed more than 21 days for the resolution of erlotinib-related toxicities to Grade 0 or 1, discontinue erlotinib and continue ARQ 197 alone.

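### In Arm 2, a Grade 3-4 nausea, vomiting, fatigue or anorexia attributed to both drugs meets two rows of 8.6 that give different erlotinib restart doses, and nothing in the documents says which row governs

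*Combined protocol and SAP*

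**What the plan says.** Section 8.6 has dedicated erlotinib rows for diarrhea, rash and interstitial lung disease. Everything else falls to two catch-all rows defined by attribution.

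- **Attributable to erlotinib, Grade 3 or 4:** "Interrupt erlotinib until resolution to Grade 0 or 1 and then restart 1 dose level lower". Footnote (c) limits this to events with at least a two-step "Grade level change from baseline".
- **Attributable to ARQ 197, Grade 3 or 4:** erlotinib is held until ARQ 197 resumes, and "If toxicity was deemed related to ARQ 197 no dose reduction of erlotinib is indicated".

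The opening paragraph of 8.5 couples the holds ("If ARQ 197 is held, erlotinib will also be held for patients on Arm 2 and resumed at the same time" as ARQ 197) and then states the waiver flatly: "There will be no dose reduction of erlotinib if the toxicity was thought to be related to ARQ 197".

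For ARQ 197 itself, 8.5b says that a patient with "Grade 3 or greater non-hematologic toxicity which resolves to Grade 0 or 1 may be treated at a next lower dose level". The step is permitted, not ordered.

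Two rules in 8.2 also bear on the point. 8.2b reads "If multiple toxicities are seen for any given single agent, administer dose based on greatest reduction required for any single toxicity observed". 8.2d adds "No dose re-escalations are allowed".

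**The concern.** The dosing rules assume that each toxicity belongs to one drug. Neither catch-all row is restricted to events attributed to that drug alone, and nor is the waiver in 8.5. The risk lists in 3.1b and 3.2b overlap heavily, so attribution to both drugs is foreseeable in Arm 2. The SPEER notes in those sections do provide for an event listed for both agents, but only to decide on expedited reporting.

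The literal waiver is the less safe of the two readings. It restarts erlotinib unreduced after, for example, Grade 3-4 vomiting that erlotinib helped to cause. The warnings in 3.2b associate severe dehydration from diarrhea, vomiting or anorexia with renal failure, some of it fatal, and name pre-existing renal disease as a risk factor. This is a renal cancer population, and 5.3e admits patients with creatinine up to twice the upper limit of normal.

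A second, smaller consequence is descriptive. Section 11.3 summarizes the frequency and extent of required dose modifications by arm. In Arm 2 that summary could partly reflect which row was followed.

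**Working it through.** The plan gives no figure to reproduce. The check traces one event through the rules and then does the dose arithmetic.

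**Step 1. How far the risk lists overlap.** The ARQ 197 list (3.1b) has 13 terms. Four are hematologic: anemia and decreased lymphocytes, neutrophils and white cells. That leaves 13 − 4 = 9. Eight of the nine are also on the erlotinib list (3.2b): diarrhea, nausea, vomiting, fatigue, anorexia, alopecia, palmar-plantar erythrodysesthesia and maculo-papular rash. Only sinus bradycardia is not. Fatigue is in the over-20% column for both drugs. These are any-grade listings.

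**Step 2. Which shared terms reach the catch-all rows.** Diarrhea and rash have their own rows. Nausea, vomiting, fatigue and anorexia do not, so they are the clear cases. The point does not rely on alopecia or palmar-plantar erythrodysesthesia.

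**Step 3. One event, two rows.** Take a first Grade 3-4 event of one of these four kinds, at least two grades above baseline, attributed to both drugs, in a patient on the starting doses in 7.1b.

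| Rule | Erlotinib during the event | Erlotinib at restart |
|---|---|---|
| 8.6, erlotinib row | Interrupted to Grade 0 or 1 | 100 mg/day |
| 8.6, ARQ 197 row, and 8.5 opening | Held until ARQ 197 resumes | 150 mg/day |

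The rows agree on interrupting erlotinib. They disagree on the restart dose.

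**Step 4. Is there a tie-breaker?**
- 8.2b ranks several toxicities of one agent. It does not address one toxicity of two agents.
- 8.7a interrupts erlotinib for severe or persistent gastrointestinal toxicity with dehydration but sets no restart dose.
- 8.6 footnotes (a) and (b) cover re-escalation, intolerance at 50 mg and non-resolution within 21 days. Footnote (c) only narrows the erlotinib row: a patient at Grade 2 at baseline who reaches Grade 3 does not trigger it, so no conflict arises there.
- 7.0 refers dose-modification questions to study contacts and dosing principles to SWOG Policy #38. That is a route to an answer, not a rule in the documents.

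**Step 5. Size, from the dose table in 8.6.**
- First event at 150 mg: (150 − 100)/150 = 33% lower under the erlotinib row.
- A patient already at 100 mg: (100 − 50)/100 = 50% lower.
- Two such events: the erlotinib row gives 150 → 100 → 50 and the waiver gives 150 → 150 → 150; (150 − 50)/150 = 67% lower. This requires both events to be attributed to both drugs, both to meet footnote (c), and the same row to be followed each time.

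These are differences in prescribed dose per patient, not effects on outcome.

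**Step 6. Frequency.** The documents give no Grade 3-4 rate for the combination by term. The combination Phase I trial in 2.0 (25 patients) reported no DLTs, and the two serious events it names, neutropenia and sinus bradycardia, are not shared terms. The number of Arm 2 patients affected cannot be calculated.

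**The case against.** The best case against is that the two rows can be read together. The ARQ 197 row may mean only that an ARQ 197 toxicity does not by itself call for cutting erlotinib. If erlotinib also caused the event, the row above applies on its own terms and the dose is 100 mg. That is a fair reading of the 8.6 wording. It fits the 8.5 sentence poorly, because that sentence flatly rules out a reduction once the toxicity is thought related to ARQ 197. The sensible reading is available, but the text does not require it.

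Second, a site in doubt has a referral route in 7.0, and Policy #38 is unseen, so nobody can say from these documents that it leaves the question open. This stands. The claim is limited to the visible text.

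Third, the harm is bounded. Both drugs are stopped until recovery, ARQ 197 may resume at 240 mg BID, 8.7a treats dehydration whatever the attribution, 8.3 and the study calendar bring patients back every two weeks for eight weeks and then every four, and 7.6 allows removal for unacceptable toxicity or at the physician's discretion. Nothing in the documents ties the renal deaths in the warnings to a restart at 150 mg rather than 100 mg. All of this stands and keeps the point modest.

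A reader might also infer more than the text supports:
- **That the diarrhea and rash rows conflict with 8.5 just as clearly.** They carry no attribution condition, so the 8.5 sentence could clash with them. But that sentence follows the coupled-hold rule and could mean only that a hold caused by ARQ 197 does not itself trigger an erlotinib reduction. This case is weaker and the point does not rest on it.
- **That many patients would be affected, or that 67% is the expected gap.** Overlapping any-grade lists are not Grade 3-4 rates, and 67% needs two qualifying events.

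**Conclusion.** The point holds as a gap in the Arm 2 dosing rules. For a Grade 3-4 nausea, vomiting, fatigue or anorexia attributed to both drugs and meeting footnote (c), the visible text supports two erlotinib restart doses and does not choose between them. Taken literally, 8.5 chooses the higher. The difference is one dose level per event (150 versus 100 mg at a first event), and it persists.

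The conclusion assumes that investigators sometimes attribute one event to both drugs, which the overlapping risk lists make likely, and that neither Policy #38 nor the contacts impose a uniform answer, which cannot be checked here. Its consequences are limited to dosing safety and consistency in Arm 2 and to the descriptive summary in 11.3.

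A reader might infer that the trial's primary conclusion is at risk. The documents do not support that: the two-stage response rule in 11.2 takes no dose-modification input, and its stated operating characteristics do not depend on which row is followed. Nor is any claim made here about patients whose toxicity outlasts 21 days, which is a separate question under 7.6c, 8.5c and 8.6 footnote (b).

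**What to change.** 1. In the opening of 8.5 and the last row of 8.6, restrict the waiver, for example: *Erlotinib is not reduced for a toxicity attributed to ARQ 197 and not to erlotinib.*
2. Add to 8.2: *Arm 2, Grade 3-4 toxicity thought related to both drugs: ARQ 197 follows 8.5; erlotinib is held while ARQ 197 is held and, unless 8.6 requires permanent discontinuation, resumes with it at the dose set by the applicable 8.6 row (including footnote c).*

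The grade limit in the second sentence matters. For Grade 2 diarrhea, 8.6 holds erlotinib while 8.5b keeps ARQ 197 at full dose, and a rule without a grade limit would misfire there. The exception for permanent discontinuation preserves the Grade 4 rash and interstitial lung disease rules.

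The cost is two sentences reworded and one added by amendment, with no new visits, data items or patients. The clinical downside is that some Arm 2 patients would have both drugs reduced for one event. The protocol pages are stamped closed effective 05/29/2014, so the practical value is for any Arm 2 patient still on treatment and for reading the 11.3 summary.

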## 8.7 Suggested management of toxicities

- a. Diarrhea. The recommended dose of loperamide is 4 mg at first onset, followed by 2 mg every 2 to 4 hours until diarrhea resolves for 12 hours. In the event of severe or persistent diarrhea, nausea, anorexia, or vomiting associated with dehydration, erlotinib therapy should be interrupted and appropriate measures should be taken to intensively treat the dehydration. Since there have been rare reports of hypokalemia and/or acute renal failure (including fatalities), secondary to severe dehydration, renal function and serum electrolytes (including potassium) should be monitored in this setting.
- b. Rash/skin toxicity. Patients should be informed that skin toxicity is to be expected during treatment with erlotinib. Skin toxicity may take the form of dry skin, rash, acneiform eruption, or hair or nail changes. Prophylactic treatment of the skin may prevent or reduce skin toxicity. The patient should be encouraged to use an alcohol-free, emollient cream applied twice a day to the entire body as soon as the patient starts therapy with erlotinib. Creams and ointments are recommended because they have a greater ability to retain moisture than lotions. Examples of suitable emollient creams include: Neutrogena® Norwegian formula, SARNA® Ultra, Vanicream™, Aveeno® (fragrance-free formulation), and Eucerin® cream. Other over-the-counter aqueous creams or emulsifying ointments may also provide symptomatic benefit. Lotions should be avoided because they often contain alcohol, which will dry the skin. Patients should also be encouraged to use a titanium dioxide or zinc oxide-based sunscreen product applied to sun-exposed areas twice per day.

Patients who develop skin toxicity and are symptomatic should be treated with topical therapy such as hydrocortisone cream or clindamycin gel. If needed, oral minocycline or oral doxycycline may be combined with the topical therapy. A topical immunomodulating cream such as Elidel could also be considered. For more severe rash, oral corticosteroids may be beneficial. Patients who fail to respond to these measures may have the dose of erlotinib interrupted or reduced.

Minocycline is known to interfere with anticoagulants and oral contraceptives. Patients treated with minocycline who are taking anticoagulants and/or oral contraceptives should be monitored accordingly.

Bullous, blistering and exfoliative skin conditions have been reported, including cases suggestive of Stevens-Johnson syndrome/toxic epidermal necrolysis, which in some cases were fatal. Interrupt or discontinue erlotinib treatment if the patient develops severe bullous, blistering, or exfoliating conditions.

- c. Ocular Disorders. Corneal perforation or ulceration has been reported during use of erlotinib. Other ocular disorders including abnormal eyelash growth, keratoconjunctivitis sicca or keratitis have been observed with erlotinib treatment and are known risk factors for corneal ulceration/perforation. Interrupt or discontinue erlotinib therapy if patients present with acute/worsening ocular disorders such as eye pain.

8.9 Adverse Event Reporting

Toxicities (including suspected reactions) that meet the expedited reporting criteria as outlined in [Section 16.0](#) of the protocol must be reported to the Operations Office, Study Chair, the NCI via CTEP-AERS, and to the IRB per local IRB requirements.

CLOSED EFFECTIVE 05/29/2014

9.0 STUDY CALENDAR

Ω √

REQUIRED STUDIES	PRE STUDY	Cycle 1		Cycle 2		Cycle 3	Cycle 4	Cycle 5	Cycle 6	Cycle 7	Follow-Up
		Wk 1	Wk 3	Wk 5	Wk 7	Wk 9	Wk 13	Wk 17	Wk 21	Wk 25	
PHYSICAL											
History & Physical Exam	X *		X	X	X	X	X	X	X	X	X
Weight and Performance Status	X		X	X	X	X	X	X	X	X	X
Disease Assessment ≠	X					X		X		X	
Toxicity Notation			X	X	X	X	X	X	X	X	
S1107 Baseline Abnormalities Form	X										
LABORATORY											
CBC/Differential/Platelets	X		X	X	X	X	X	X	X	X	
Bilirubin	X		X	X	X	X	X	X	X	X	
SGOT & SGPT	X		X	X	X	X	X	X	X	X	
Serum Creatinine	X		X	X	X	X	X	X	X	X	
Electrolytes (see Section 5.3f )	X		X	X	X	X	X	X	X	X	
Pregnancy Test (if applicable)	X										
TISSUE SAMPLES											
Archived tissue sample (see Section 15.0 )	X										
X-RAYS AND SCANS											
X-rays/Scans as needed for disease measurement ≠	X					X		X		X	X
TREATMENT Δ											
ARM 1											
ARQ 197		X	X	X	X	X	X	X	X	X	
ARM 2											
ARQ 197		X	X	X	X	X	X	X	X	X	
Erlotinib		X	X	X	X	X	X	X	X	X	

Click here for [FOOTNOTES](#)

**NOTE:** Forms are found on the protocol abstract page on the SWOG website ([www.swog.org](http://www.swog.org)). Forms submission guidelines are found in [Section 14.0](#).

#### FOOTNOTES

- \* Physical exam and medical history must be completed within 28 days prior to registration (see [Section 5.3a](#)).
- △ Continuous oral daily dosing (see [Section 7.1](#)).
- Ω Protocol treatment and parameters will continue at these intervals until off protocol treatment per [Section 7.6](#). While on protocol treatment, disease assessments will continue every 8 weeks until progression. If patient is removed from protocol treatment prior to disease progression, assessments will be continued on this schedule until disease progression.
- √ After disease progression, follow-up will occur (with lab tests and scans performed at the discretion of the treating investigator) every 3 months for the first year and then every 6 months thereafter for up to three years after registration or until death.
- ≠ Tumor assessment will be done after every second cycle by the same method used at baseline. REMEMBER, RESPONSE SHOULD BE CONFIRMED BY A SECOND DETERMINATION AT LEAST 4 WEEKS AFTER A COMPLETE OR PARTIAL RESPONSE HAS BEEN NOTED.

CLOSED EFFECTIVE 05/10/16

## 10.0 CRITERIA FOR EVALUATION AND ENDPOINT DEFINITIONS

### 10.1 Measurability of lesions

a. **Measurable disease:** Measurable disease is defined differently for lymph nodes compared with other disease and will be addressed in a separate section below.

1. Lesions that can be accurately measured in at least one dimension (longest diameter to be recorded) as  $\geq 2.0$  cm by chest x-ray, by  $\geq 1.0$  cm with CT or MRI scans, or  $\geq 1.0$  cm with calipers by clinical exam. All tumor measurements must be recorded in decimal fractions of centimeters (or millimeters).

The defined measurability of lesions on CT scan is based on the assumption that CT slice thickness is 0.5 cm or less. If CT scans have slice thickness greater than 0.5 cm, the minimum size for a measurable lesion should be twice the slice thickness.

2. **Malignant lymph nodes** are to be considered pathologically enlarged and measurable if it measures  $\geq 1.5$  cm in **SHORT AXIS** (greatest diameter perpendicular to the long axis of the lymph node) when assessed by scan (CT scan slice recommended being no greater than 0.5 cm).

b. **Non-measurable disease:** All other lesions (or sites of disease), including small lesions (longest diameter  $< 1.0$  cm or pathologic lymph nodes with  $\geq 1.0$  cm to  $< 1.5$  cm short axis), are considered non-measurable disease. Bone lesions, leptomeningeal disease, ascites, pleural/pericardial effusions, lymphangitis cutis/pulmonitis, inflammatory breast disease, and abdominal masses (not followed by CT or MRI), are considered non-measurable as are previously radiated lesions that have not progressed.

c. **Notes on measurability**

1. For CT and MRIs, the same type of scanner should be used and the image acquisition protocol should be followed as closely as possible to prior scans. Body scans should be performed with breath-hold scanning techniques, if possible.
2. PET-CT: At present, the low dose or attenuation correction CT portion of a PET-CT is not always of optimal diagnostic CT quality for use with RECIST measurements. However, if the site can document that the CT performed as part of a PET-CT is of identical diagnostic quality to a diagnostic CT, then the CT portion of the PET-CT can be used for RECIST measurements and can be used interchangeably with conventional CT.
3. Ultrasound: Ultrasound is not useful in assessment of lesion size and should not be used as a method of measurement.
4. Cystic lesions that meet the criteria for radiographically defined simple cysts should not be considered as malignant lesions (neither measurable nor non-measurable) since they are, by definition simple cysts.
5. If a target lesion becomes very small some radiologists indicate that it is too small to measure. If the lesion is actually still present, a default measurement of 0.5 cm should be applied. If the radiologist believes the lesion has gone, a default measurement of 0.0cm should be recorded.

## 10.2 Objective status at each disease evaluation

Objective Status is to be recorded at each evaluation. All measurable lesions up to a maximum of 2 lesions per organ 5 lesions in total, representative of all involved organs, should be identified as target lesions at baseline. All other lesions (or sites of disease) including any measurable lesions over and above the 5 target lesions should be identified as non-target lesions. Measurements must be provided for target measurable lesions, while presence or absence must be noted for non-target measurable and non-measurable disease.

For studies that use disease progression as an endpoint, whole body scanning at specific intervals is necessary to determine that progression is NOT present outside of the “target” areas. Therefore, in these studies it is not acceptable to image only the “target” areas of the body in follow-up scans. For study-specific imaging requirements, see the Study Calendar in [Section 9.0](#).

- a. **Complete Response (CR):** Complete disappearance of all target and non-target lesions (with the exception of lymph nodes mentioned below). No new lesions. No disease related symptoms. Any lymph nodes (whether target or non-target) must have reduction in short axis to < 1.0 cm. All disease must be assessed using the same technique as baseline.
- b. **Partial Response (PR):** Applies only to patients with at least one measurable lesion. Greater than or equal to 30% decrease under baseline of the sum of appropriate diameters of all target measurable lesions. No unequivocal progression of non-measurable disease. No new lesions. All target measurable lesions must be assessed using the same techniques as baseline.
- c. **Stable:** Does not qualify for CR, PR, Progression or Symptomatic Deterioration. All target measurable lesions must be assessed using the same techniques as baseline.
- d. **Progression:** One or more of the following must occur: 20% increase in the sum of appropriate diameters of target measurable lesions over smallest sum observed (over baseline if no decrease during therapy) using the same techniques as baseline, as well as an absolute increase of at least 0.5 cm. Unequivocal progression of non-measurable disease in the opinion of the treating physician (an explanation must be provided). Appearance of any new lesion/site. Death due to disease without prior documentation of progression and without symptomatic deterioration (see [Section 10.2e](#)).

Notes regarding new lesions: FDG-PET imaging can complement regular scans in identifying new lesions according to the following algorithm.

1. Negative FDG-PET at baseline, with a positive FDG-PET at follow-up is a sign of progression based on a new lesion.
2. No FDG-PET at baseline and a positive FDG-PET at follow-up corresponding to a potential new site of disease must have a confirmation by anatomical assessment (e.g. CT, MRI, x-ray) as new site of disease to be considered progressive disease. In such a case, the date of progressive disease will be the date of the initial abnormal FDG-PET.

- e. **Symptomatic deterioration:** Global deterioration of health status requiring discontinuation of treatment without objective evidence of progression. Efforts should be made to obtain objective evidence of progression after discontinuation.
- f. **Assessment inadequate, objective status unknown.** Progression or symptomatic deterioration has not been documented, and one or more target measurable lesions have not been assessed or inconsistent assessment methods were used.
- g. Objective status notes:
1. Non-measurable and non-target measurable disease do not affect Objective Status in determination of CR (must be absent--a patient who otherwise has a CR, but who has non-measurable or non-target measurable disease present or not assessed, will be classified as having a PR). However, non-measurable and non-target lesions are included in determination of progression (if new sites of disease develop or if unequivocal progression occurs in the opinion of the treating physician).
  2. An objective status of PR or stable cannot follow one of CR. Stable can follow PR only in the rare case that tumor increases too little to qualify as progression, but enough that a previously documented 30% decrease no longer holds.
  3. In cases for which initial flare reaction is possible (hypercalcemia, increased bone pain, erythema of skin lesions), objective status is not progression unless either symptoms persist beyond 4 weeks or there is additional evidence of progression.
  4. Lesions that appear to increase in size due to presence of necrotic tissue will not be considered to have progressed.
  5. For bone disease documented on bone scan only, increased uptake does not constitute unequivocal progression. However, increase in the soft tissue component of a lesion as measured by CT or MRI would constitute progression.
  6. Appearance of new pleural effusions does not constitute unequivocal progression unless cytologically proven of neoplastic origin, since some effusions are a toxicity related to therapy or other medical conditions. Increase in the size of an existing effusion does not constitute unequivocal progression, since the fluid status of the patient could alter the size of the effusion.
  7. If CR determination depends on a lesion for which the status is unclear by the required tests, it is recommended the residual lesion be investigated with biopsy or fine needle aspirate.

